**B. Visit #2 - On-Therapy Evaluations (Study Days 5-7)**

The investigator should assess the overall clinical progress of the subject and adverse events.

1. Physical exam, including vital signs
2. Evaluate subject for signs and symptoms of pneumonia
3. Assess adverse events
4. Pharmacokinetics (see Appendix II for instructions)
5. Assess drug compliance

**C. Visit #3 - Post-Therapy Evaluation (Study Days 2-4 After Completion of Therapy)**

The investigator should assess the subject's overall clinical progress and assess adverse events.

Clinical response will be determined by comparing a subject's post-therapy signs and symptoms to those observed on admission as well as by comparing post-therapy chest x-ray findings with those on admission, as follows:

Cure:	Resolution of signs and symptoms associated with active infection along with resolution of chest x-ray findings
Improved:	Incomplete resolution of signs, symptoms, and chest x-ray findings
Failure:	No response to therapy
Unable to Evaluate:	Due to the administration of non-study antimicrobials, I insufficient course of therapy, subject not returning for post-therapy evaluation, etc.

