## **DESCRIPTION OF STUDY**

This is a multicenter, prospective, randomized, Phase III study to evaluate the safety and efficacy of Drug A compared with cefuroxime axetil in the treatment of community-acquired pneumonia in adults.

Investigators will collectively enroll approximately 450 outpatient subjects with community-acquired pneumonia to ensure clinically evaluable data from 400 subjects. The study will be terminated when 200 clinically evaluable subjects per treatment group have been prospectively enrolled. The study may be amended if necessary to ensure enrollment of sufficient numbers of subjects with infections due to critical pathogens. The data will be pooled across investigators for safety and efficacy analyses. A subject is eligible for study entry if the infection was acquired in a community setting.

Subjects who meet all the inclusion criteria and exhibit none of the exclusion criteria may be enrolled. A Potential Subject Roster, which will document the initials of each patient considered for study entry, the date of assessment, severity of diagnosis and the reasons for not enrolling any potential study subject, will be maintained at each site. As subjects qualify for the study, subject numbers will be assigned in strict sequential order at each site. Subjects will receive one of two treatment regimens according to a computer-generated randomization schedule prepared by the CCRP Pharmaceuticals, Inc. and kept at the individual investigational sites. This randomization schedule will provide for equal numbers of subjects in the two regimens. The random study group assignment will be provided for each subject in individually sealed envelopes. As a qualified subject enters the study, the next available randomization envelope in the sequence will be opened to reveal the appropriate therapy regimen. The following two regimens will be used:

- 1. Drug A 500 mg PO q12h**
- 2. Cefuroxime axetil 500 mg PO q12h**

Total therapy duration will be 7 to 14 days, as clinically indicated. A minimum of five days of therapy will be required for analysis of microbiologic response, unless subjects have failed clinically and have taken sufficient drug to be considered evaluable within this time. If, in the opinion of the investigator, a subject requires more than 14 days of therapy (e.g., *Legionella pneumophila*, slowly resolving pneumonia, etc.) the medical monitor should be contacted.

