All subjects will be assessed for possible adverse events during the course of the study. All adverse events will be documented on the case record form. Safety will also be assessed by the physical examinations and laboratory tests performed pre-therapy and post-therapy.

Efficacy will be assessed by microbiological and clinical response. Microbiological data will be obtained from cultures of respiratory secretions.

Clinical response will be evaluated by assessing physical exam signs and symptoms, laboratory results, and chest X-ray findings by the investigator after the completion of therapy.

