**D. Visit #4 - Post-Study Evaluation (Study Days 21-28 After Completion of Therapy)**

1. Physical exam, including vital signs
2. Evaluate subject for signs and symptoms of pneumonia
3. Culture and Gram stain of respiratory secretions, if still positive at Visit #3 (Study Days 2-4 After Completion of Therapy)
4. Repeat chest x-ray, if pneumonia not resolved at Visit #3 (Study Days 2-4 After Completion of Therapy)
5. Clinical response will be assessed by comparing the subject's pre-study signs and symptoms (including pre-study chest x-ray findings) to those observed post-therapy:
  - Cure - resolution of signs and symptoms associated with active infection, along with resolution of chest x-ray findings
  - Improved - continued incomplete resolution of signs and symptoms with no deterioration or relapse during the follow-up period
  - Failure - no response to therapy
  - Relapse - resolution or improvement of signs and symptoms at the post-therapy evaluation with reappearance or deterioration of signs and symptoms of infection.
  - Unable to Evaluate - due to the administration of non-study antimicrobials, subject not returning for post-study evaluation, etc.
6. Assess adverse events

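### For clinical response, Unable to Evaluate overlaps with Failure and no precedence is stated, so treatment failures can drop out of the evaluable set on which the study is sized and stopped

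*Protocol*

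**What the plan says.** **Visit #3 (Protocol, Section V.C).** Clinical response is Cure, Improved, Failure or Unable to Evaluate (UE). Failure is defined only as "No response to therapy". UE applies as follows: "Due to the administration of non-study antimicrobials, I insufficient course of therapy, subject not returning for post-therapy evaluation, etc".

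**Visit #4 (Section V.D).** The category recurs without the short-course reason: "Unable to Evaluate - due to the administration of non-study antimicrobials, subject not returning for post-study evaluation, etc".

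**Early failures (Description of Study, repeated in Section 2.2 E).** "A minimum of five days of therapy will be required for analysis of microbiologic response", with the exception "unless subjects have failed clinically and have taken sufficient drug to be considered evaluable within this time". Both the minimum and the exception are written for microbiologic response. How much drug is sufficient is not stated.

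**Sizing and stopping (Description of Study).** Enrolment is planned around the evaluable count: "Investigators will collectively enroll approximately 450 outpatient subjects with community-acquired pneumonia to ensure clinically evaluable data from 400 subjects". The end of the study is tied to that count in each arm: "The study will be terminated when 200 clinically evaluable subjects per treatment group have been prospectively enrolled". Section VIII gives the same 200 per group for the chi-square comparison and names no analysis population.

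**Who rates.** Clinical response rests on signs and symptoms, "laboratory results, and chest X-ray findings by the investigator after the completion of therapy". The randomization envelope is opened to reveal the regimen, and no blinding is described.

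**Early withdrawal.** Section V.E requires the Visit #3 procedures at withdrawal. Their list ends with the evaluation of clinical response, and Appendix I marks that evaluation in the early-withdrawal column.

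**The concern.** The UE reasons describe events, not why they happened. In pneumonia, a switch to another antibacterial or a stopped course often follows from the drug not working. A subject who dies before Visit #3 literally fits the non-return reason. If these subjects are rated UE and the comparison is made among evaluable subjects, the exclusion occurs after randomization and is related to outcome. Response rates can then be too high. If more failures are lost from the worse arm, a real difference between the drugs shrinks or disappears. The rater can know the regimen, so the choice between the two labels need not fall equally on the arms.

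**Working it through.** **1. Do the categories overlap?** Take a subject who does not respond and is given a non-study antibacterial before Visit #3.

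- Under Failure, the subject qualifies, having shown no response.
- Under UE, the subject also qualifies, having received a non-study antimicrobial.
- Sections V.C and V.D contain no rule of precedence.
- The only clause that keeps early failures in is limited to microbiologic response.

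The rating is therefore left to the investigator.

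**2. The plan's own allowance.** 450 enrolled less 400 evaluable leaves 50, and 50/450 = 11.1%. As a check, 400/(1 − 50/450) = 450. The 200 per group cannot be reproduced, because Section VIII gives no response rates, difference or margin.

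**3. Inputs for the illustrations.** Allocation is 1:1 (Section 2.2 E), so 450 subjects means 225 per arm. The only success rate in the protocol is about 90%, for earlier use of Drug A (Section 1). All other rates and UE splits below are assumptions.

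**4. Unequal UE counts within the allowance (15 versus 35, assumed).**

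- Evaluable: 189/210 = 90.0% versus 171/190 = 90.0%, p = 1.0.
- UE as non-response: 189/225 = 84.0% versus 171/225 = 76.0%. The pooled rate is 360/450 = 0.80, SE = √(0.80 × 0.20 × 2/225) = 0.0377, z = 0.08/0.0377 = 2.12, p = 0.034.

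**5. The same share of failures dropped in both arms.** With failure rate f and share k of failures rated UE, the rate seen is (1 − f)/[(1 − f) + f(1 − k)]. For k = 0.5:

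- f = 0.10: 0.90/0.95 = 94.7%
- f = 0.20: 0.80/0.90 = 88.9%

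True rates of 90% versus 80%, 225 per arm, two-sided 0.05, pooled test without continuity correction:

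| Share of failures rated UE | Rates seen | Difference (points) | UE in total | Power |
|---|---|---|---|---|
| 0 | 90.0% vs 80.0% | 10.0 | 0 | 84.6% |
| 25% | 92.3% vs 84.2% | 8.1 | 17 | 75% |
| 50% | 94.7% vs 88.9% | 5.8 | 34 | 59% |
| 75% | 97.3% vs 94.1% | 3.2 | 51 | 35% |

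The last row uses about the whole planned allowance.

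**6. The other direction (25 UE in each arm, assumed).**

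- Evaluable: 180/200 = 90.0% versus 160/200 = 80.0%, 10.0 points, p = 0.005.
- UE as non-response: 180/225 = 80.0% versus 160/225 = 71.1%, 8.9 points, p = 0.028.

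Here the evaluable difference is the larger one.

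**7. UE unrelated to outcome.** The evaluable rates are then unbiased and the only cost is power: for 90% versus 80%, 80.2% at 200 per arm against 84.6% at 225.

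**The case against.** The strongest reply is that the text is ambiguous and does not itself remove failures. Failure is a category of its own, and the UE list does not say that it overrides an observed Failure. Response is rated at early withdrawal, so a non-responder who is stopped can be rated Failure on the spot. This stands, and it rules out any claim that failures must be lost. It does not settle the matter, because the same subject still meets a UE reason and the protocol does not say which label prevails.

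A reader might infer more than the protocol supports:

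- **That UE subjects are excluded from the efficacy comparison.** No section says so. The sizing and stopping rule implies an evaluable analysis, but not that it is the only one, and a statistical analysis plan that is not shown may define others.
- **That both response rates are inflated.** This requires UE subjects to respond less often than evaluable ones. Subjects who do not return may be cured, and antimicrobials may be given for other conditions. Step 6 shows that the evaluable difference can also be the larger one.
- **That recoding at Visit #4 undoes a Visit #3 Failure in the efficacy comparison.** Item 11 of the Protocol Summary sets efficacy at 2 to 4 days after therapy, so Visit #4 is secondary here.
- **That a subject who worsens is not a Failure as worded.** Worsening can naturally be read as no response. The gap is only that worsening and death are not named.

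It is also fair that the UE splits are chosen for illustration. Item 4 of the Protocol Summary describes the 400 as subjects who met the criteria, so some of the 50 may be eligibility losses. Finally, the protocol states no non-inferiority margin, so it does not establish that a shrunken difference would favour Drug A.

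**Conclusion.** The point holds in conditional form. For clinical response, a subject whose non-study antimicrobial, short course or non-return came from lack of response fits both Failure and UE. The protocol gives no precedence, and the rater is not described as blinded. Failures rated UE can leave the evaluable set that governs sizing and stopping.

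The possible size is material. Under the assumed 15 versus 35 split, which stays within the planned 50 of 450, an 8-point difference disappears. With half of the failures rated UE in both arms, a true 10-point difference appears as 5.8. Both figures rest on assumed rates and on UE subjects being non-responders; the protocol does not predict either pattern, and the opposite effect is possible. This should be fixed, but it does not show that the planned comparison is biased.

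**What to change.** 1. In Sections V.C and V.D, state that Failure takes precedence over UE. A subject who receives a non-study antibacterial or has a short course because of insufficient response, or who worsens or dies of the pneumonia, is classified as Failure.
2. Carry a Visit #3 Failure forward to Visit #4.
3. Keep UE for reasons unrelated to response.
4. In Section VIII, report an analysis of all randomized, treated subjects with UE as non-response beside the clinically evaluable analysis.

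This changes outcome classification only, not treatment. The cost is protocol and case report form wording, one more analysis, less favourable quoted response rates, and possibly some dilution of the difference in the all-randomized set. It should be settled before data are collected.

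Two further steps are not part of this recommendation because each is a trade-off. Ending enrolment at a fixed number randomized could leave fewer than 200 evaluable subjects per arm, and requiring the two analyses to agree can cost power.

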**The following will be performed:**

1. Physical examination, including vital signs
2. Evaluate subject for signs and symptoms of pneumonia
3. Culture and Gram stain of respiratory secretions
4. Obtain venous blood samples and urine studies listed for baseline visit
5. Repeat chest x-ray
6. Assess adverse events
7. Instruct subjects to contact the investigator immediately if they experience a return of symptoms
8. Urinalysis

9. Evaluate clinical response

**D. Visit #4 - Post-Study Evaluation (Study Days 21-28 After Completion of Therapy)**

1. Physical exam, including vital signs
2. Evaluate subject for signs and symptoms of pneumonia
3. Culture and Gram stain of respiratory secretions, if still positive at Visit #3 (Study Days 2-4 After Completion of Therapy)
4. Repeat chest x-ray, if pneumonia not resolved at Visit #3 (Study Days 2-4 After Completion of Therapy)
5. Clinical response will be assessed by comparing the subject's pre-study signs and symptoms (including pre-study chest x-ray findings) to those observed post-therapy:
  - Cure - resolution of signs and symptoms associated with active infection, along with resolution of chest x-ray findings
  - Improved - continued incomplete resolution of signs and symptoms with no deterioration or relapse during the follow-up period
  - Failure - no response to therapy
  - Relapse - resolution or improvement of signs and symptoms at the post-therapy evaluation with reappearance or deterioration of signs and symptoms of infection.
  - Unable to Evaluate - due to the administration of non-study antimicrobials, subject not returning for post-study evaluation, etc.
6. Assess adverse events

**E. Early Withdrawal from the Study**

In the event a subject withdraws from therapy prematurely, the same procedures as in Visit #3 (Study Days 2-4 After Completion of Therapy) should be performed at the time of study withdrawal. The reason for early therapy withdrawal should be documented on the appropriate case record form. Schedule follow-up visit, if appropriate.

To date approximately 150 subjects have been given Drug A. The most frequently reported side effects are outlined in the table below:

Possible Risk/Side Effect	How often has it	How serious is it?
---------------------------	------------------	--------------------

	occurred	
Nausea	It is expected to occur	Can be easily treated
Diarrhea	It is expected to occur	Can be easily treated
Vomiting	It is uncommon	Can be treated
Changes in certain levels in your blood chemistry	It is uncommon	Very Serious
Dizziness	It occasionally occurs	Can be treated
Restlessness	It occasionally occurs	Can be treated
Tremors	It occasionally occurs	Can be treated
Headache	It is expected to occur	Can be easily treated
Rash	It occasionally occurs	Can be treated

**Allergic reaction to any antibiotic in the past should be documented or noted by the investigator or the study coordinator because the study subject may have an allergic reaction to antibiotics used in this study. These allergic reactions may be life threatening.**

The risks of drawing blood from a vein includes discomfort at the site of the needle stick, possible bruising and swelling around the site of the needle stick, rarely an infection, and uncommonly feeling faint from the procedure.”

The risks of Drug A and Cefuroxime axetil to an unborn child are unknown. Therefore, if the study subject is capable of giving birth to or fathering a child, he/she should use adequate birth control measures while on the study. These measures may include abstinence, oral contraceptives (birth control pills), IUD, diaphragm, Norplant, approved hormone injections, condoms, or documentation of medical sterilization.

This research study involves exposure to radiation from chest x-rays. The amount of radiation exposure from this procedure(s) is equivalent to a uniform whole body exposure of 10 millirems. This is equivalent to 5 % of the amount of natural environmental radiation the average person receives annually. The risk from radiation exposure of this magnitude is too small to be detected in this population.

Severe and Unanticipated Adverse Events:

A severe unanticipated adverse effects are any that is severe and not stated above.

A serious Adverse event is any that is

## **VI. STUDY DRUG ADMINISTRATION**

Equal numbers of subjects will be assigned to each treatment regimen according to a computer-generated randomization schedule prepared by the sponsor. The following two regimens will be utilized:

1. Drug A 500 mg tablets PO q12h for 7-14 days

2. Cefuroxime axetil 500 mg tablets PO q12h for 7-14 days

**A. Dosage Adjustment**

Dosages of both drugs should be adjusted for subjects with a calculated creatinine clearance less than or equal to 50 ml/min. These subjects should receive an initial loading dose of 500 mg po and then subsequent doses as follows:

Creatinine Clearance	Drug Dose	Dose Interval
20-50 ml/min	500 mg	48 hours

When only serum creatinine data are available, the following formula (based on sex, weight, and age of the subject) may be used to estimate the creatinine clearance. The serum creatinine should represent a steady state of renal function.

**Males:**  $\frac{\text{weight (kg)} \times (140 - \text{age [in years]})}{72 \times \text{serum creatinine (mg/100 ml)}}$

**Females:** 0.85 x above value

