## **1. BACKGROUND AND RATIONALE**

Drug, A is an investigational compound in the quinolone class of antibiotics. It- has been used in Europe for 5 years for treating patients with community-acquired bacterial pneumonia, with success rates around 90%.

Although Drug A is more active in vitro than other members of its class, toxicity profiles in animal studies are similar. Accordingly, Drug A is expected to offer an opportunity to enhance the efficacy profile of quinolones without an incremental increase in adverse events.

It is anticipated that Drug A could be used once daily for many infections including mild to moderate skin, lower respiratory, and pelvic infections, as well as UTIS. Severe or life-threatening infections could be treated with a twice-daily dosing schedule.

To date, approximately 150 subjects have received Drug A in Phase I and Phase II trials in the United States. Adverse reactions were judged probably or possibly drug-related in 14.8% of courses; drug treatment had to be stopped prematurely in 3.5%. The most frequent reactions were gastrointestinal complaints (chiefly nausea, diarrhea, and vomiting), metabolic disorders (elevated SGOT, SGPT, serum creatinine or blood urea nitrogen), nervous system effects (dizziness, restlessness, tremor, and headache), and rash.

In animal toxicologic trials, Drug A and other quinolones appear to have similar safety profiles. The absorption, distribution, metabolism, and excretion appear to be similar as well, both in animals and in humans. Based on these studies, it is anticipated that the fate of administered Drug A will be comparable to that of other long acting quinolones both with respect to human safety and tolerance.

Over 40 million people have been treated with various quinolones. They have generally been well tolerated. The events considered likely to be drug-related in clinical trials in subjects receiving multiple doses were nausea, headache, dizziness, and diarrhea.

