### C. Exclusion Criteria

1. Subjects infected with a resistant organism known prior to starting therapy
2. Previous allergic or serious adverse reaction to any members of the quinolone class of antimicrobials, or a severe reaction to penicillin or any cephalosporin
3. Severe renal failure (creatinine clearance < 20 ml/min)
4. Presence of neutropenia (< 500 WBC's/mm^3)
5. Pregnant women or nursing mothers
6. Use of an investigational agent within 30 days prior to entry into the study
7. Previous treatment under this protocol

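### The shared renal dosing row gives cefuroxime axetil 500 mg every 48 hours from 50 ml/min downward, which under-exposes comparator subjects in the upper part of the band on every assumption tried

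*Protocol*

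**What the plan says.** Protocol section VI sets the same standard dose in each arm: "Drug A 500 mg tablets PO q12h for 7-14 days" and "Cefuroxime axetil 500 mg tablets PO q12h for 7-14 days".

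Section VI.A then states: "Dosages of both drugs should be adjusted for subjects with a calculated creatinine clearance less than or equal to 50 ml/min". It continues: "These subjects should receive an initial loading dose of 500 mg po and then subsequent doses as follows". The table that follows has a single row: creatinine clearance 20-50 ml/min, dose 500 mg, interval 48 hours. It does not separate the drugs and has no step within the band. The exclusion criteria (section 2.2 C) bar only clearance below 20 ml/min, so the whole band may enrol.

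The only kinetic rationale is in section 1, and it concerns Drug A: "it is anticipated that the fate of administered Drug A will be comparable to that of other long acting quinolones". The same section anticipates once-daily use of Drug A for many infections, including mild to moderate lower respiratory infection. The protocol does not describe how cefuroxime axetil is eliminated or where its renal adjustment comes from.

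**The concern.** A quinolone and a cephalosporin share one renal schedule, and the kinetic statements in the protocol speak to the quinolone only. For the comparator, a fourfold cut starts abruptly at 50 ml/min and stays the same down to 20 ml/min, although clearance itself changes 2.5-fold over that range (50/20).

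The people at stake are outpatients with pneumonia who are randomised to cefuroxime axetil and whose clearance lies in the upper part of the band. After baseline, their next scheduled check is Visit #2, on Study Days 5-7. By then the rule has given them 3-4 doses, against 10-14 on the standard schedule. The microbiologic analysis would not single them out, because its minimum is set in time: "A minimum of five days of therapy will be required for analysis of microbiologic response". Three doses over five days meet it as well as ten do.

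Such subjects are easy to picture. There is no upper age limit, and by the protocol's own formula an 80-year-old, 60 kg woman with serum creatinine 1.0 mg/100 ml has a clearance of 0.85 × 60 × (140 − 80)/(72 × 1.0) = 42.5 ml/min. She is only an illustration; the protocol does not say how many subjects would fall in the band.

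**Working it through.** **Inputs from the protocol.** Standard dose 500 mg every 12 h (section VI). Renal dose 500 mg, then 500 mg every 48 h, for 20-50 ml/min (section VI.A). Entry limit 20 ml/min (section 2.2 C).

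**Inputs assumed, because the protocol gives none.** Linear kinetics. Renal share of total clearance f = 0.5 to 1. Reference subject with clearance ref = 80 to 120 ml/min. Average exposure as the yardstick.

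**Step 1: the dose cut.** Standard: 500 × 24/12 = 1000 mg/day. Renal: 500 × 24/48 = 250 mg/day. Ratio 4.0. Doses counted from hour 0, standard versus renal: 5 days, 10 vs 3; 7 days, 14 vs 4 (7000 vs 2000 mg, 3.5-fold because of the first dose); 14 days, 28 vs 7 (14000 vs 3500 mg, 4.0-fold).

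**Step 2: exposure against a reference subject on the 12-hourly dose.**

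Relative exposure = 0.25 / [(1 − f) + f × CrCl/ref]

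At ref = 100 ml/min:

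| CrCl (ml/min) | f = 1 | f = 0.75 | f = 0.5 |
|---|---|---|---|
| 50 | 50% | 40% | 33% |
| 40 | 62.5% | 45% | 36% |
| 30 | 83% | 53% | 38% |
| 25 | 100% | 57% | 40% |
| 20 | 125% | 62.5% | 42% |

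Other references with f = 1, at 50/40/30/20 ml/min:
- ref = 80: 40%, 50%, 67%, 100%
- ref = 120: 60%, 75%, 100%, 150%

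The extremes at 50 ml/min are:
- highest (f = 1, ref = 120): 0.25/(50/120) = 60%
- lowest (f = 0.5, ref = 80): 0.25/(0.5 + 0.5 × 50/80) = 0.25/0.8125 = 31%

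**Step 3: where the 48-hour interval would match.** Setting relative exposure to 1 gives f = 0.75/(1 − CrCl/ref).
- With f = 1, the match is at CrCl = 0.25 × ref: 20, 25 or 30 ml/min for ref 80, 100 or 120.
- At the bottom of the band (20 ml/min), the renal share needed is 1.00, 0.94 or 0.90 for those references.
- Above 30 ml/min, no f up to 1 and no ref up to 120 reaches parity.

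**Step 4: the interval that would hold exposure with 500 mg doses.** Interval = 12/[(1 − f) + f × CrCl/ref] hours. With f = 1 and ref = 100 it is 24 h at 50 ml/min, 30 h at 40, 40 h at 30, 48 h at 25 and 60 h at 20. With f = 0.5 it is 16 to 20 h across the band.

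**Step 5: the step at the threshold.** Compare 51 ml/min on the 12-hourly dose with 50 ml/min on the 48-hourly dose. If clearance is wholly renal, average exposure falls 4 × 50/51 = 3.92-fold. If none of it is renal, it falls 4.0-fold. This comparison needs no reference subject.

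**Step 6: Drug A against once-daily use.** Section 1 gives no once-daily dose, so 500 mg is assumed. Relative exposure = 0.5/[(1 − f) + f × CrCl/100]. At 50/40/30/20 ml/min, f = 1 gives 100%, 125%, 167%, 250%; f = 0.75 gives 80%, 91%, 105%, 125%; f = 0.5 gives 67%, 71%, 77%, 83%.

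**The case against.** The strongest reply is that no wrong dose has been shown. The protocol gives no elimination data for cefuroxime axetil, and a protocol need not reproduce a comparator's dosing information. The row contradicts nothing else in the text, and every clearance figure above is an assumption. This stands in part: a reader might infer that 500 mg every 48 hours is proven wrong for cefuroxime axetil, and the document cannot prove that. But the result for the upper part of the band does not hang on one choice of inputs. It holds over the whole range tried, including the case kindest to the row. Dosing instructions are also protocol content, not something left to an analysis plan.

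A second reply is that Drug A is not under-dosed. This largely stands. Against an assumed 500 mg once daily, the row gives at least full exposure across the band when clearance is wholly renal. A reader might take the fourfold cut as equally damaging in both arms; section 1 does not support that.

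A third reply is that the rule is the same in both arms and that Visit #2 and the early-withdrawal procedures would catch failing subjects. Those checks help, but they do not correct what subjects are given first. A reader might also infer a bias in favour of Drug A. Neither the renal shares nor the number of subjects at 20-50 ml/min is stated, so no bias can be sized or even signed. Counting the evaluability minimum in days is not an error in itself either, since a dose count could exclude subjects correctly treated at long intervals.

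**Conclusion.** The point holds for the comparator. Under linear kinetics, a renal share of 0.5-1 and a reference clearance of 80-120 ml/min, a cefuroxime axetil subject at 50 ml/min receives 31% to 60% of the average exposure that the trial's 12-hourly dose gives a reference subject (50% at a 100 ml/min reference with wholly renal clearance). Every clearance above 30 ml/min falls short. The 48-hour interval matches only at about 20-30 ml/min, and only if clearance is almost wholly renal. In that most favourable case the row can exceed reference exposure at the bottom of the band, so the shortfall is established for the upper part only.

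This is a matter of subject protection and should be settled before anyone at or below 50 ml/min is dosed. It does not establish the right dose of either drug, how many subjects are affected, or any distortion of the comparison.

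**What to change.** In section VI.A, replace the shared row with two entries, one for Drug A and one for cefuroxime axetil. Each should state its own threshold, dose and interval, verified against that drug's own dosing information. Split the 20-50 ml/min band, for example at 30 ml/min, so that the 48-hour interval is not applied to comparator subjects in the upper part unless that information supports it. The 30 ml/min cut comes from the assumptions above and is illustrative; no particular dose is proposed.

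The cost is one table amendment and possibly a short delay in enrolling subjects at or below 50 ml/min while the two entries are verified.
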